#### 9.3 Indicate the gender of participants being enrolled into this study:

- Male
- Female
- Both male and female

#### 9.4 Inclusion/Exclusion Criteria

What are the inclusion and exclusion criteria for study participation?

The only inclusion criterion for participation is the minimum age requirement (18 years old).

There are no exclusion criteria for participation in the baseline study (part 1). However, participants who do not follow the instructions for the specific writing task will be unable to sign-up for the remaining follow up sessions (Parts 2-6) and will be excluded from the final data analyses. For Part 1, they will be provided with a link to the Qualtrics survey. For Parts 2-5, participants will be able to sign up after successfully completing the prior session; however, if they do not successfully complete the writing prompt requirements outlined in Part 1, then they will be unable to continue on to the remaining study sessions (parts 2-6). If this is the case, then the researchers involved in this study will contact participants to let them know their remaining follow-up sessions will be canceled, but will still receive credit for what they have completed.

Do the exclusion criteria exclude specific populations or individuals based on gender, culture, language, economics, race, or ethnicity?

Yes  No

If Yes, then justify each exclusion:

#### 9.5 Describe the setting where the informed consent process will take place (e.g. classroom, clinic, laboratory, office, park, personal computer, etc.).

If a waiver of documentation of informed consent is requested, then describe how participants will review the information sheet.

Before beginning Part 1 of the study, Qualtrics will present participants with the online informed consent.

Participants who check "I agree" to indicate that they consent to their participation in the study will be allowed to participate in the study and be asked to provide their TAMU email. Before beginning each follow up part (Parts 2-6), participants will see the same informed consent form on Qualtrics once again and check "I agree" once again before starting the follow up sessions and be asked to provide their TAMU email once again.

#### 9.6 Experience of Subjects

Describe the experience of subjects while participating in this research. (Please describe what the participant will experience from the time of learning of the study through completion.)

Participants (undergraduate students at TAMU who need to participate in research for class credit) will sign up to participate in the study by using the SONA subject participation pool. After signing up for Part 1, online participants will receive a link to a Qualtrics survey. Those who are completing the study in lab will participate on the day they signed up for. After reading information about the study and consenting electronically by clicking "I agree", participants will report their TAMU email and then continue on to complete the Part 1 questionnaires. This should take 30 minutes of their time and they will receive 1 credit toward their class research requirement for completing Part 1.

After completing Part 1, participants will be allowed to participate in the follow up sessions (parts 2-6) if they correctly and completely fulfilled the writing task requirements. Each follow up session will be completed through Qualtrics and should not exceed 30 minutes for each follow up session. Each follow up session will take place one week after the previous session. A summary of this is below:

**Part 1: Baseline**

**Part 2: First follow up (One week after baseline)**

**Part 3: Second follow up (One week after Part 2)**

**Part 4: Third follow up (One week after Part 3)**

**Part 5: Fourth follow up (One week after Part 4)**

**Part 6: Fifth follow up (One week after Part 5)**

*Note: If there is not enough time in the semester, some participants may not complete all follow-ups; they will complete the number of sessions and follow ups described in their consent forms*

How long will the participants be engaged in the research (length of time, e.g., 15 minutes, 45 minutes on Day 1, 60 minutes on Day 2, etc.)?

30 minutes for Part 1 (week 1)  
30 minutes for Part 2 (week 2)  
30 minutes for Part 3 (week 3)  
30 minutes for Part 4 (week 4)  
30 minutes for Part 5 (week 5)  
30 minutes for Part 6 (week 6)

## 10.0

### Privacy and Confidentiality

#### 10.1 How will the identities of subjects be protected in all research records? The information collected/analyzed is:

*Note: Data that are coded, where the key to the code is accessible to researchers, are considered confidential information and subject to privacy regulations.*

- Anonymous: The identity of the participant cannot readily be determined by the investigator AND the identity of the participant is not connected to information gathered.
- Confidential: Research participants can be identified; however, information gathered will be protected.
- Neither: Research participants can be identified, and information gathered may be connected to the participant.

Summarize procedures to protect the confidentiality and anonymity of participants (e.g., replies coded, etc.).

Pre-screen data will be collected as part of the larger Psychology Subject Pool pre-screen survey conducted by the department and managed by the Psychology Subject Pool Coordinator. The pre-screen survey is distributed via the SONA system and participants complete the pre-screen survey on their own time and on their own device, wherever they are comfortable. All data is maintained in the SONA system (which can only be accessed by the Psychology Subject Pool Coordinator). At the completion of the pre-

screen period, the Subject Pool Coordinator will give PI access to the pre-screen results for the AUDIT questions. The PI will store the pre-screen data on the Liberal Arts IT computer servers (see description below).

Participants data will initially be saved using their TAMU email as identification codes, which will allow us to connect data from Part 1 of the study to data from Parts 2-6 of the study. However, for extra safety precautions, once the data set has been collected and assembled, we will delete participant emails and replace them with randomized participant ID numbers.

All data (pre-screen and study data) is housed on Liberal Arts IT computer servers at Texas A&M University. These servers are physically protected by a 24/7 armed security guard and multiple physical barriers that require card/fingerprint/keys to pass through. Physical access is limited to the Liberal Arts Server team members and is reviewed every year. To access the share requires a campus IP address or VPN access, and also membership in the active directory group that is allowed access to that particular folder. Only researchers involved with this study will have access to the particular IT server folder where data will be stored.

What are the plans for retention and/or destruction of linkages between study data and personal identifying information? (Specify when and how personal identifying information will be destroyed.)

TAMU emails will be deleted and changed to randomized participant ID numbers once the study data has been collected and compiled. No identifying information, including names, will be collected as the online information sheet system only requires participants check "I agree" to consent to their participation.

If these linkages will not be destroyed, explain how you will maintain confidentiality of the personally identifying information.

If personally identifying information will not be kept confidential, then justify and explain the informed consent process for sharing this information.

Will a Certificate of Confidentiality (through DHHS or another Federal agency) be utilized?

<https://humansubjects.nih.gov/coc/index>

Yes  No

## 11.0

## Potentially Sensitive Subject Matter and Procedures

### 11.1 Will this type of information be collected?

Yes  No

### 11.2 Select all that describe the information.

- No sensitive matters
- Abortion
- Alcohol
- Body composition
- Criminal activity
- Depression
- HIV/AIDS
- Learning disability
- List of current medications
- Medical/dental problems
- Medical history
- Potential child abuse/neglect
- Psychology/psychiatry
- Sexual activity

- Suicide
- Unethical behavior
- Other

If other, please specify:

If Medical History or Mental Health History information will be collected, please describe:

### 11.3 Deception

Will deception be used as part of the study?

Yes  No

If Yes, please describe the deception.

Please describe the debriefing procedures to be used.

Debriefing procedures will occur after Part 6 of the study. After the final survey, Qualtrics will show participants a debriefing sheet that will include additional information pertaining to the aims and implications of the study. We will also provide a list of resources (which will appear on Qualtrics), both on and off TAMU's College Station campus, that are available to students should they need extra support.

Provide justification for the deception.

## 12.0

### Risks and Benefits

#### 12.1 Regulatory definition of minimal risk is that the probability and magnitude of harm or discomfort anticipated in the research are not greater in and of themselves than those ordinarily encountered in daily life or during the performance of routine physical or psychological examinations or tests (45 CFR 46.102(h)(i)).

Identify the types of risk associated with participation in the study:

- Physical
- Privacy
- Confidentiality
- Psychological/emotional
- Social
- Legal
- Other

If Other, please describe the risks:

If participants are under the legal drinking age or disclose illegal activities while under the influence of alcohol, there might be additional risk.

Describe the potential risks or discomforts to participants. Include justification of the known risks, which were selected above.

A mild stress reaction may be experienced by the part of the study that involves writing about a negative alcohol event but this should be comparable to disclosing any negative event during the course of a day. Furthermore, in the consent form, participants will be told that they will be asked to write about a negative alcohol event and be reminded that they are free to discontinue their participation at any time. In some individuals, this stress reaction may be greater and we will provide resources for all participants, in case they need extra support after discussing their negative alcohol event. Questionnaires may also cause minimal amounts of distress, since some encourage participants to think about, and thus be in-tune with their levels of distress.

Describe the approaches you will take to minimize these risks and/or to minimize their impact.

All participants will be provided with resources that they can utilize should they feel distressed by the study. Instructions will be given to participants before beginning the writing task to leave out specific locations, names, and other personally identifiable information. Finally, the writing about a negative event involving alcohol will be emphasized in the consent forms and participants who do not feel comfortable writing about this will be asked not to participate. They will also be asked to take the study in a place they feel is private and comfortable for them to discuss sensitive topics, such as alcohol use and consumption. In addition, the consent form will remind participants that they are free to discontinue their participation in the study at any time, should they feel uncomfortable or distressed.

What alternatives are available to subjects outside the research (i.e., what is the standard of care, is the research intervention available without participating)?

Students are provided with alternative assignments that can be completed in lieu of research participation by their professors. Furthermore, participants may choose any of the other studies available on the TAMU SONA system as alternatives to participating in our study.

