All follow up parts will be either online or in the lab, one week apart. Participants will indicate, for each day the previous week (Sunday, Saturday, Friday, Thursday, Wednesday, Tuesday, Monday), what they were doing, their general location, if they consumed alcohol that day, and the extent to which they experienced a list of situations. Following this, all participants will then indicate the extent that they used the list of PBS. For those who had been randomly assigned to the counterfactual condition in Part 1, they will complete additional measures: indicating the use of the counterfactual strategies that the participant came up with in Part 1 and their intention to use these counterfactual strategies over the next week. Finally, all participants will complete a measure of perceived behavioral control, rate intentions to use PBS in the next week, and answer the protective behavioral strategy norms questions. In follow up sessions 4 and 6, participants will also complete the Personal Assessment of Responsible Drinker Identity Scale and the delay discounting task. Email information will be completed at the end of each part. A page displaying additional resources will also be displayed. All participants will finish the study by completing a debriefing task after the final follow up.

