**Post-manipulation measures**

Task 9: Perceived behavioral control

Task 10: PBS Intentions

Task 11: Perceptions of Protective Behavioral Strategies questions

Task 12: Alcohol Use contemplation/intention measure

Task 13: Email

Task 14: Additional Resources

Follow Up Parts 2-6

Task 1:PBS-20

Task 2: Daily indication of drinking and strategy use

Task 3: Counterfactual Behavior Use and Intentions

Task 4: Perceived behavioral control

Task 5: PBS Intentions

Task 6: Perceptions of Protective Behavioral Strategies questions

Task 7: PARDI [only follow up sessions 4 and 6]

Task 8: Delay Discounting Measure [only follow up sessions 4 and 6]

Task 9: Email

Task 10: Additional Resources

(End of Part 6): Debriefing

**Demographics.** A basic demographics questionnaire will collect data on participants' age, gender, ethnicity, race, language spoken, and fluency in English.

**Alcohol Use Disorder Identification Test** (AUDIT; Saunders, Aasland, Babor, De La Fuente, & Grant, 1993). Participants will complete the Alcohol Use Disorder Identification Test – Consumption Scale (AUDIT-C), which is a screener for alcohol consumption. Previous studies support the reliability and validity of the AUDIT-C as a measure of alcohol consumption among college students (DeMartini & Carey, 2012).

**Daily Drinking Questionnaire-Revised** (DDQ-R; adapted from Collins, Parks, & Marlatt, 1985) Assesses drinking habits and patterns among individuals averaged over the last 3 months.

**Perceived Behavioral Control.** (PBC; Cooke, Sniehotta, & Schuz, 2007; Ajzen & Sheikh, 2013) This measure is on a 7-point scale and is composed of six items: For me to avoid drinking alcohol is (difficult-easy); I am confident that, if I wanted to, I could avoid alcohol (definitely false-definitely true); How much control do you believe you have over avoiding alcohol (no control- complete control)? For me to drink less than 7(females)/10 (males) units in a single session in the next week would be (very difficult-very easy). If I wanted to I could drink less than 7(females)/10(males) units in a single session in the next week (definitely false-definitely true). How much control do you believe you have over drinking less than 7(females)/10(males) units in a single session in the next week? (no control-complete control).

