## Participants

Participants will be recruited via the Texas A&M University online research subject pool (SONA). To be included in the study procedures and subsequent data analyses, participants must be 18 or older and complete all parts. There are no exclusion criteria for participation in the baseline study (part 1). However, participants who do not follow the instructions for the specific writing task will be unable to sign-up for the remaining follow up sessions (Parts 2-6) and will be excluded from the final data analyses. For Part 1, they will be provided with a link to the Qualtrics survey (if completing online) or will sign up via SONA for an in-person lab session. For Parts 2-5, participants will be able to sign up after successfully completing the prior session; however, if they do not successfully complete the writing prompt requirements outlined in Part 1, then they will be unable to continue on to the remaining study sessions (parts 2-6). If this is the case, then the researchers involved in this study will contact participants to let them know their remaining follow-up sessions will be canceled, but will still receive credit for what they have completed.

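### Support resources promised to all are shown only at the end of each part, so someone who stops during Part 1 has no described route to them; debriefing timing also needs reconciling

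*Protocol*

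**What the plan says.** Section 12.1 of the Protocol accepts that writing about a negative alcohol event may cause a stress reaction, which could be more than mild in some people. It answers: "we will provide resources for all participants, in case they need extra support after discussing their negative alcohol event". Under the measures to reduce risk it repeats the commitment: "All participants will be provided with resources that they can utilize should they feel distressed by the study". It adds that the consent form reminds participants that "they are free to discontinue their participation in the study at any time, should they feel uncomfortable or distressed".

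Delivery is set out in section 8.1. The post-manipulation list for Part 1 ends with "Task 14: Additional Resources". The list for Parts 2-6 places the same page last, as Task 10, ahead only of the debriefing that closes Part 6. The Procedure narrative mentions the page only after the email item that ends each part.

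Section 11.3 says: "Debriefing procedures will occur after Part 6 of the study". It adds that a resource list will be provided as well. The Procedure narrative in section 8.1 says instead: "All participants will finish the study by completing a debriefing task after the final follow up". Section 9.6 warns: "If there is not enough time in the semester, some participants may not complete all follow-ups". Section 15.2 provides for waves of 4 or 5 sessions. For participants who fail the writing task, the researchers "will contact participants to let them know their remaining follow-up sessions will be canceled" (section 8.1, Participants); credit for completed work is kept.

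**The concern.** The resource list is the only support that section 12.1 describes for someone who is already distressed. The other measures there are advance warnings, a private setting, leaving identifying details out of the writing, and freedom to stop. If the list can be reached only by finishing the session, it may miss a person who uses the freedom to stop because the task upset them. The two commitments, resources for all and stopping at any point, would then fail together in the case they were written for.

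Debriefing is a second, smaller matter. If it is tied to Part 6, a wave that ends at Part 4 or 5 never reaches it.

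What is at stake is a stated participant protection. Nothing here touches the multilevel model or the hypotheses in the SAP.

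**Working it through.** There is no stated figure to reproduce and no formula applies. The check is to follow each way of leaving the study through the task order in section 8.1.

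**Order within Part 1.** Consent; pre-manipulation measures; manipulation (event writing in Conditions 1 to 3, normative feedback in Condition 4); four post-manipulation measures (Tasks 9 to 12); email (Task 13); resources (Task 14).

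**Exit routes.**

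| Route | Resource page | Debriefing |
|---|---|---|
| Stops during Part 1, e.g. on the writing page | Not reached | Not reached |
| Completes Part 1, then cancelled for the writing task | Seen once (Task 14) | None described |
| Stops between later sessions, or during one | Seen at the end of every completed part, so at least once | None described |
| Wave of 4 sessions | Seen 1 + 3 = 4 times | Depends on which wording governs |
| Wave of 5 sessions | Seen 1 + 4 = 5 times | Depends on which wording governs |
| Completes Parts 1-6 | Seen 1 + 5 = 6 times | Yes |

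Only the first route misses both.

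**Is there another way to the list on that route?** The only exit screen described is for people who decline consent (section 8.1, Informed Consent; section 18.3), and it is not said to carry resources. No withdrawal page is described. Sections 8.1 and 8.2 allow remote completion, so a staff member need not be present; for lab sessions no hand-over of the list is described either.

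**Can early leavers be contacted?** Sections 9.5 and 9.6 have the email address given right after consent, which would make this possible. Section 8.1 lists email as Task 13, after the writing. If only the second is true, someone who stops on the writing page has left no address in the survey.

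**Debriefing.** Section 11.3 and the section 8.1 task list place it after Part 6. The Procedure narrative places it after the last follow-up, for everyone. For a six-session participant these coincide. For a 4- or 5-session wave they do not, because there is no Part 6. Neither wording describes a debriefing for people cancelled after Part 1 or for dropouts.

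**The case against.** **The consent form may already give the resources.** It is attached to the application but is not in the text reviewed, and section 9.5 says it is shown again before every part. If it lists support services, the Part 1 gap is largely closed and section 12.1 need only say so. This stands, and the conclusion is conditional on it. The resource page itself could not be read either, so what it contains is unknown.

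**A reader might infer that everyone cut off early gets neither resources nor debriefing.** The documents do not support that. Participants cancelled after completing Part 1, those in short waves and those who drop out later have all passed the resource page at least once.

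**A reader might also infer that every short-wave participant misses debriefing.** That follows only if the Part 6 wording governs. The Procedure narrative says otherwise, and section 11.3 itself goes on to describe the sheet as shown once the last survey is done. Section 9.6 treats the shorter schedule as planned and described in the consent form. This is an inconsistency with a natural resolution, not a proven omission. Section 11.3 describes the sheet as covering aims and implications, and no deception is described, so missing it is a lesser loss than missing the resource list.

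**It is tempting to attach a number.** Assuming equal allocation, 1,500 × 3/4 = 1,125 people would do the event writing, and an assumed 1% to 5% stopping there would be about 11 to 56 people. Neither the allocation ratio nor the rate is in the documents, and section 12.1 expects a mild reaction, so this range is not evidence of size.

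**A support link on the writing page could intrude on the manipulation.** This is fair: such a link would sit within the task and ahead of the intention measures. It bears on where the list goes, not on whether it should come earlier.

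**Conclusion.** The point holds in a limited form. As described, a participant who stops during Part 1 has no route to resources that section 12.1 promises to all, unless the consent form supplies them. This follows from the task order and needs no assumed rate. How many people it would affect cannot be estimated.

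For everyone who completes Part 1, only debriefing is in question. Its timing is inconsistent for 4- and 5-session waves, and it is not described for cancelled participants or dropouts. On its own that would be a minor reconciliation.

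The Part 1 gap is worth correcting because the change costs almost nothing and makes a stated safeguard work as promised. It does not bear on the validity of the trial's results.

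**What to change.** 1. Show the existing resource list before the manipulation, on the Part 1 consent or information page, identically in all four arms, and keep it on the last page. If the consent form already carries it, state that in section 12.1. Placing it at consent keeps it out of the writing task.
2. Email the list to anyone who starts Part 1 but does not finish it. For this, reconcile sections 9.5 and 9.6 with Task 13 in section 8.1, and confirm that the address is collected before the writing task.
3. Reconcile section 11.3 and the section 8.1 task list with the Procedure narrative, so that debriefing follows each participant's own last scheduled session (Part 4, 5 or 6).
4. Attach the debriefing sheet and resource list to the cancellation notice, and send both to incompletes when their credit is granted by hand (section 16.5).

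Cost: a minor IRB amendment, a changed display trigger in Qualtrics and standard email texts. Participants would see a resource list slightly earlier, equally in every arm.
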